In Stage 1, Group 1 participants who do not meet Step 2 entry criteria, all Group 2 participants and all Group 3 participants will be referred to the South African TB Control Programme for treatment. In Stage 2, Group 1 participants who do not meet Step 2 entry criteria, Group 2 participants who do not meet Step 2 entry criteria, and **Group 3 participants who do not meet Step 2 entry criteria** will be referred to the South African TB Control Programme for treatment.

In Step 2, prior to initiation of treatment, sputum will be collected for quantitative culture on solid medium (for **CFU for Groups 1 and 2 only**) and liquid medium (for determination of **TTD for all groups**) and for MIC determination and phenotypic DST. In addition to GenoType MTBDRplus, GenoType MTBDRsI, which identifies additional mutations associated with resistance to fluoroquinolones **and injectable TB medicines**, will be performed on sputum of participants with MDR-TB (but not INH-monoresistant TB) who are enrolled in the study. Sixteen-hour sputum collections will be performed daily during INH treatment, as per standard EBA methodology [42]. Sampling for PK analysis will be performed at steady state on Day 6 (± 1). NAT2 genotyping will be performed on a blood sample to help explain variability in INH PK parameters, and a saliva sample will be collected for evaluation of a new rapid NAT2 genotyping test. Safety and tolerability will be monitored via clinical evaluations throughout the study and through scheduled laboratory evaluations.

To avoid unnecessary delay in initiating TB treatment, screening evaluations for Step 1 and Step 2 may occur on the same day.

To minimize risk to study staff and study participants, participants with MDR-TB will be hospitalized on a different ward from participants with DS-TB or INH-monoresistant TB. Strict infection control practices will be followed, including the wearing of N95 masks where appropriate and hospitalization on wards with negative pressure ventilation. In addition, persons with a previous known exposure to XDR-TB or those who have been treated previously for MDR-TB, and thus have a higher risk of XDR-TB, will not be included in this study.

The study will proceed in two stages, as follows:

Stage 1—Pilot study to ensure feasibility:

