6.0 CLINICAL AND LABORATORY EVALUATIONS

6.1 Schedule of Events

6.1.1 **Table 6.1-1:** Step 1

Evaluation	Screening	Step 1 Day 0 ²
Spot Sputum Collection	X	X ³
AFB Microscopy	X	
Genotypic DST with HAIN MTBDRplus	X	
Culture and Phenotypic DST Determination with MIC		X
Hospitalization ¹	X	

¹At the discretion of the investigator, some participants may be hospitalized during the screening evaluations, but this is not a requirement.

²The screening and Step 1 Day 0 visits may be combined for these participants.

³Step 1 Day 0 spot sputum collection is only required if the screening spot sputum is insufficient or inadequate for Step 1 entry evaluations.

6.1.2 Table 6.1-2: Step 2

Evaluation	Screening	Pre-entry	Entry: Registration/ Randomization	Study Treatment (Days)							Discharge	Final Visit	Premature Discontin- uation	
				Step 2 Day 0	1	2	3	4	5	6	7			
NAT2 genotype (blood and saliva)			X											
Chest X-ray	X ²													
Spot Sputum Collection			X ³											
Genotypic DST (MTBDRs) ⁴			X											
Overnight Sputum Collection		X	X	X	X	X	X	X	X	X	X			
EBA Analysis by Solid Culture CFU (Groups 1 and 2 only) Determination and Liquid MGIT Culture for TTD ⁵ (all groups)		X	X	X	X	X	X	X	X	X	X			
Pharmacokinetic Sampling										X				
Hospitalization	X ⁶	X	X	X	X	X	X	X	X	X	X			

¹Participants must have a negative serum or urine pregnancy test within 7 days prior to entry.

²A chest x-ray is not required at screening if results of a chest x-ray performed within 14 days prior to screening are available.

³Sputum from Step 1 (Screening or Day 0) may be used if there is an adequate amount for genotypic DST.

⁴For those participants who have MDR-TB identified by MTBDRplus.

⁵X's here refer to the date that the overnight sputum collection was begun. Assay will be conducted the next morning.

⁶At the discretion of the investigator, some participants may be hospitalized during the screening evaluations, but this is not a requirement.

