9.6.2 Analyses of Secondary Endpoints

9.6.2.1 INH PK parameters will be estimated using noncompartmental analysis and the descriptive statistics will be reported by NAT2 genotype status (See [section 10.0](#)).

9.6.2.2 The distribution of INH MIC against *M. tuberculosis* isolates with *inhA* mutation, *katG* mutation, or neither of these mutations will be reported.

9.6.2.3 The AUC/MIC that achieves 50% of the mean EBA in Group 2 will be estimated and designated the “Target AUC/MIC”. A Monte Carlo simulation will be performed using the MIC distribution (Group 1), NAT2 genotype distribution (Groups 1 and 2), and distribution of AUC values (Groups 1 and 2) associated with each dose and put to estimate the proportion of participants who have TB with an *inhA* mutation in a population would be expected to achieve the target AUC/MIC with 5, 10, or 15 mg/kg daily. **As exploratory analysis, the same analysis will be performed for Group 3 to determine which proportion of individuals with TB with a *katG* mutation would be expected to achieve the target AUC/MIC with a dose of 15 or 20 mg/kg daily.**

9.6.2.4 The same analysis below will be conducted separately based on \log_{10} CFU and TTD. If the number of phases is the same for every dosing **cohort**:

- **Six bi-exponential models for \log_{10} CFU and four bi-exponential models** will be fit in order to estimate the “early” and “late” phase slopes for each **cohort**. Since this is an INH mono-therapy study, there may be an inflection point at Day 2 after the initiation of INH treatment.

If the number of phases is not the same for every dosing **cohort**:

- **Six linear or nonlinear mixed effect models for \log_{10} CFU and four linear or nonlinear mixed effect models for TTD** will be fit in order to estimate treatment effect for each **cohort**.
- (For \log_{10} CFU only): Another approach will be taken to utilize the area between baseline CFU per mL and the CFU curve (ABBCC) for each participant, as measured using the trapezoidal rule. Since baseline CFU per mL may differ substantially between **groups**, the ABBCC will be expressed as a proportion of the total area under the baseline CFU per mL. The descriptive statistics will be reported **for each cohort**.

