### **2.4 Primary Objectives**

1. Estimate the 7-day EBA, based on CFU counts, of INH among participants infected with TB with inhA mutations taking one of three doses of INH (5, 10, or 15 mg/kg daily), and participants infected with DS-TB taking standard-dose INH (5 mg/kg daily).
2. Estimate the 7-day EBA, based on time-to-detection (TTD), of INH among participants infected with TB with inhA mutations taking one of three doses of INH (5, 10, or 15 mg/kg), participants infected with TB with katG mutations taking 15 or 20 mg/kg daily, and participants infected with DS-TB taking standard-dose INH (5 mg/kg daily).
3. Determine the association between the area under the curve (AUC)/MIC of INH and the EBA of INH among participants with smear-positive pulmonary TB.
4. Describe the safety and tolerability of doses of 5, 10, and 15 mg/kg of INH administered daily among participants with sputum smear-positive pulmonary TB.

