## 3 Definitions

### 3.1 Analysis Population

Safety population: Safety analyses will be intent-to-treat and include all eligible participants who took at least one dose of study drugs.

Efficacy population: The primary analyses will use a per-protocol approach, limited to participants who provide CFU and TTD data at both study entry and Day 7. For the model based analysis, all randomized participants who had at least one CFU count or TTD will be included.

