## 4.3 Analyses of Outcomes Measures

### 4.3.1 Primary outcomes

This is a per-protocol analysis in the efficacy population defined in Section 3.1. The primary endpoint is EBA0-7(CFU), which is defined in Section 3.2. Descriptive statistics of EBA0-7(CFU) with N, mean (s.d.), median (IQR), min, and max for each of the cohorts will be reported. Box plot of EBA0-7(CFU) with Q1, median, mean, and Q3 and plot with 95% confidence intervals for the mean EBA0-7(CFU) will be created for each cohort. Note: The analysis for this outcome will be performed for Group 1 and Group 2.

Another primary endpoint is EBA0-7(TTD), which is defined in Section 3.2. Descriptive statistics of EBA0-7(TTD) with N, mean (s.d.), median (IQR), min, and max will be reported by each cohort. Box plot of EBA0-7(TTD) with Q1, median, mean, and Q3 and plot of 95% confidence interval for the mean EBA0-7(TTD) will be created for each cohort.

New grade 2 or higher signs and symptoms, as well as laboratory events will be summarized in a table using SMR. In addition, all new grade 2 or higher signs/ symptoms and laboratory events with relatedness of treatment and most related drugs.

The PK analysis to examine the relationship between the AUC/MIC and the EBA as described in the protocol Section 9.2.1.2 will be provided in a separate PK analysis plan.

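### The SAP's single primary efficacy population requires CFU as well as TTD, so read literally it admits no Group 3 participant to the primary TTD analysis

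*SAP*

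**What the plan says.** SAP 3.1 gives one efficacy population for the primary analyses: "limited to participants who provide CFU and TTD data at both study entry and Day 7". SAP 4.3.1 adopts it at the start, before either endpoint is named: "This is a per-protocol analysis in the efficacy population defined in Section 3.1". Within 4.3.1 a note confines EBA0-7(CFU) to Groups 1 and 2. EBA0-7(TTD) carries no such limit: "Descriptive statistics of EBA0-7(TTD) with N, mean (s.d.), median (IQR), min, and max will be reported by each cohort".

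The SAP says in 1.1 and 2.2 that it rests on Protocol Version 3.0. That version does no CFU count for Group 3. Protocol 3.0 describes solid culture as for "CFU for Groups 1 and 2 only", and the Step 2 schedule in Protocol 6.1.2 lists "EBA Analysis by Solid Culture CFU (Groups 1 and 2 only) Determination and Liquid MGIT Culture for TTD", with TTD marked for all groups. Protocol 6.3.9 and endpoints 9.2.1.1 and 9.2.1.2 draw the same line.

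Group 3 nevertheless belongs to the primary TTD analysis. Primary objective 2 in SAP 2.4 covers the inhA cohorts, "participants infected with TB with katG mutations taking 15 or 20 mg/kg daily, and participants infected with DS-TB taking standard-dose INH". Protocol 9.6.1.2 plans six confidence intervals for EBA0-7(TTD), and SAP 5 sets aside a second primary report for Group 3 under Version 3.0.

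Two neighbouring rules also matter. For the model-based analysis, SAP 3.1 says that "all randomized participants who had at least one CFU count or TTD will be included". Protocol 9.6.2.4 plans six models for CFU "and four linear or nonlinear mixed effect models for TTD".

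**The concern.** The population rule joins two assays with *and*, and one of those assays is not performed in Group 3. Applied as written, the rule leaves the katG cohorts without a primary efficacy set, and their TTD result is the only primary efficacy result that Version 3.0 was written to add. The analyst of the Group 3 report would have to depart from the stated population to produce its main table, with no sentence in the SAP to cite for doing so.

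The same rule ties the two endpoints together in Groups 1 and 2. A participant with complete TTD but no usable CFU at entry or Day 7 leaves the TTD analysis too, and the reverse also holds.

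**Working it through.** **Inputs.** Planned evaluable numbers come from the sample-size section of the protocol schema and from Protocol 9.4: Group 1 has 16 in each of three dose cohorts, Group 2 has 16, and Group 3 has 10 in each of two dose cohorts. Which assay each group has comes from Protocol 3.0, 6.1.2 and 9.2.1.

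**Step 1: reproduce the plan's total.** 3 × 16 + 16 + 2 × 10 = 84. This matches the minimum evaluable total in Protocol 9.1, which therefore counts the 20 in Group 3.

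**Step 2: apply the SAP 3.1 rule cohort by cohort**, assuming no missing samples.

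| Cohort | Planned n | CFU done | TTD done | In set if both are required | In set if TTD alone is required |
|---|---|---|---|---|---|
| Group 1, 5 mg/kg | 16 | yes | yes | 16 | 16 |
| Group 1, 10 mg/kg | 16 | yes | yes | 16 | 16 |
| Group 1, 15 mg/kg | 16 | yes | yes | 16 | 16 |
| Group 2, 5 mg/kg | 16 | yes | yes | 16 | 16 |
| Group 3, 15 mg/kg | 10 | no | yes | 0 | 10 |
| Group 3, 20 mg/kg | 10 | no | yes | 0 | 10 |
| Total | 84 | | | 64 | 84 |

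The literal rule keeps 64 of 84 overall and 0 of 20 in Group 3. Four cohorts are non-empty, so four of the six intervals in Protocol 9.6.1.2 can be drawn.

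**Step 3: repeat with enrolled numbers.** The clarification memo of 12 December 2019 gives 44 in Group 1 Step 2, 16 in Group 2 Step 2 and a target of 20 in Group 3 Step 2, so 44 + 16 + 20 = 80. The literal rule admits at most 44 + 16 = 60. Group 3 is again 0 of 20.

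**Step 4: look for an exception.** The Group 3 rule in SAP 3.2 removes contaminated and re-cultured results and says nothing on CFU. The note in SAP 4.3.1 limits the CFU endpoint to Groups 1 and 2 but does not alter the population used for TTD. The SAP 2.5 remark about CFU data being available for katG is attached to a secondary objective. None of these changes 3.1.

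**Step 5: count the models.** Cohorts with CFU: 3 + 1 = 4. Cohorts with TTD: 3 + 1 + 2 = 6. Protocol 9.6.2.4 has six for CFU and four for TTD, so the two counts are reversed.

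**The case against.** The best defence is that the rule should be read distributively, with CFU data needed for the CFU endpoint and TTD data for the TTD endpoint. Much of the text supports that as the intention: objective 2 names the katG doses, endpoint 9.2.1.2 is marked for all groups, six intervals are planned, SAP 3.2 has a culture rule written only for Group 3, and a whole report is devoted to that group. This stands as evidence of intent. It does not repair the wording. The next sentence of SAP 3.1, on the model-based set, joins the assays with *or*, and that contrast favours taking *and* at face value in the sentence before it.

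It can also be said that Group 3 TTD is still analysed in the mixed models, and that Protocol 9.4 calls the per-cohort Group 3 analysis exploratory. Both are true. The models are secondary, however, and objective 2 and endpoint 9.2.1.2 remain listed as primary.

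A reader might infer more than the documents support:

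- **That the katG objective cannot be analysed, or that any repair is post hoc.** The endpoint is fully defined and the data are collected. The post hoc clause in SAP 4.1 concerns changes to outcome measures, and correcting who enters the analysis leaves EBA0-7(TTD) as defined.
- **That two TTD cohorts go unmodelled.** Protocol 9.6.2.4 and SAP 4.3.2 both call for a model for each cohort, so the reversed counts lose none.
- **That the non-randomized Group 2 is dropped from the models.** SAP 4.3.2 names Group 2 for the CFU models and fits TTD models for each cohort. The word *randomized* is loose, but it removes nobody.
- **That a loss rate can be put on Groups 1 and 2.** The documents give no assay failure rate. Both assays use the same pooled overnight sputum, so failures cannot be treated as independent. Participants who cannot supply required samples are discontinued and replaced, and Version 2.0 used duplicate TTD with one surviving value accepted.

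**Conclusion.** The point holds as a defect in a stated rule. SAP 3.1, applied as written through SAP 4.3.1, puts 0 of 20 planned Group 3 participants into a primary analysis that the objectives, the endpoint definition and the reporting plan all require. It reduces the planned TTD set from 84 to 64.

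The result rests on two things only: the literal reading of the population sentence, and Version 3.0's decision not to do CFU in Group 3. It needs no assumption about missing data, variance or effect size. The intended analysis is not in doubt, so what is at risk is the traceability of the Group 3 primary result to a written rule.

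For Groups 1 and 2 the joint requirement is a real feature of the rule, but its effect in this trial is unknown. SAP 5 says their report was completed in September 2018, so the question there is which rule was used. The reversed model counts and the word *randomized* are minor inconsistencies.

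**What to change.** In SAP 3.1, replace the single efficacy population with two:

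- **CFU-evaluable:** Groups 1 and 2, with log10 CFU at baseline and Day 7. Used for EBA0-7(CFU). Planned size 64.
- **TTD-evaluable:** all groups, with TTD at baseline and Day 7. Used for EBA0-7(TTD). Planned size 84, including 20 of 20 in Group 3.

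SAP 4.3.1 should then name the set for each endpoint. Apply the definition to the Version 3.0 Group 3 report. For the completed 2018 report on Groups 1 and 2, state which rule was used; this point does not require redefining its population.

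Two consistency edits can go in at the same time. In the model-based sentence of SAP 3.1, refer to all participants enrolled in Step 2, so that the assigned Group 2 cohort is plainly covered. In Protocol 9.6.2.4, correct the counts to four models for CFU and six for TTD.

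The cost is a SAP revision and a short protocol clarification. No new data, samples or participants are needed.

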### 3.2 Endpoint Definitions

The following is the calculation of log 10 transformed CFU/mL sputum at each time point.

- $\log_{10} \text{CFU/mL} = \log_{10}[(\text{average of CFU/mL}_A \text{ and CFU/mL}_B) \times (\text{dilution factor}) \times 10^{(\text{Dilution})}]$  where the dilution factor is set to 20. CFU/mLA and CFU/mLB are measured from the same sputum sample at a time point.

Example: If CFU/mLA = 150, CFU/mLB = 185, and dilution = 4, then  $\log_{10} \text{CFU/mL} = 7.53$

When multiple TTD results were obtained for a specimen (per Protocol Version 2.0 but not Protocol Version 3.0), the following is the calculation of total TTD.

- The final TTD is the mean of TTDA and TTDB. TTDA and TTDB are measured from the same

sputum sample at a time point. If one of the TTD is missing, the other TTD will be used as the final TTD. In a rare case of observing TTD = 42 days, the sites will determine if the value should be used as is or treated as missing.

The following are definitions from Section 9.2 of the protocol document.

- EBA0-7(CFU)= [baseline log10 CFU/mL sputum (mean of log10 CFU/mL at pre-entry and day 0) – log10 CFU/mL at day 7]/7. For a CFU/ml count of 0, the log10 CFU/mL will be set to 0
- EBA0-7(TTD)= [baseline TTD (mean of TTD at pre-entry and day 0) – TTD at day 7]/7
- EBA0-2(CFU)= [baseline log10 CFU/mL sputum (mean of log10 CFU/mL at pre-entry and day 0) – log10 CFU/mL at day 2]/2. For a CFU/ml count of 0, the log10 CFU/mL will be set to 0
- EBA0-2 (TTD)= [baseline TTD (mean of TTD at pre-entry and day 0) – TTD at day 2]/2.
- EBA2-7(CFU)= (log10 CFU/mL sputum at day 2 – log10 CFU/mL at day 7)/5. For a CFU/ml count of 0, the log10 CFU/mL will be set to 0
- EBA2-7 (TTD)= [TTD at day 2 – TTD at day 7]/5

For Group 3, TTP results from contaminated samples and from TTP from re-culture results after an additional decontamination step will be excluded from analysis.

## 4 Statistical Methods

### 4.1 General Considerations

Baseline characteristics will be summarized by cohorts (by Group and treatment arm) but with no statistical comparisons comparing cohorts.

Categorical data will be summarized using N (%), and continuous data using N, min, Q1, median, Q3, max, and mean (STD) (when appropriate). Nonlinear mixed model using SAS procedure NLMIXED will be used to estimate the decrease of log10 CFU counts per day for the 'early' and 'terminal' phase as well as the increase of TTD per day. If there is no clear bi-phase pattern, linear mixed model using SAS procedure MIXED will be used. For TTD, log10 transformation may be applied if appropriate. Any modifications to outcome measures after the team has seen data collected after entry will be considered as post hoc.

The primary endpoint analysis is defined in Section 4.3.1; however, the secondary modeling approach, which is described in Section 4.3.2, might be more appropriate in case of missing CFU or TTP outcomes at baseline and Day 7.

### 4.2 Visit Schedule and Analysis Windows

- Screening visit window = within 2 weeks (14 days) prior to Step 1 entry

- Pre-entry visit window = approximately 2 days prior to Step 2 entry
- Step 2 entry visit = Day 0 in Step 2
- On-Treatment evaluations: conducted between Day 1 and Day 7. Participants will be discharged on Day 8.
- Post-Treatment evaluations: completed in a period of plus or minus 3 days from Day 21.

**Note:** Participants who do not complete 7 days of study treatment or who cannot provide at least 1 mL for all required overnight sputum samples through Day 7 will be discontinued from the study, and replaced.

- Schedule of Events

Evaluation	Screening	Pre-entry	Entry: Registration/ Randomization	Study Treatment (Days)							Discharge	Final Visit	Premature Discontinuation	
				Step 2 Day 0	1	2	3	4	5	6	7			
Documentation of HIV status	X													
Medical/Medication History			X											
Complete Physical Examination	X													
Targeted Physical Examination			X	X	X	X	X	X	X	X	X	X	X	X
Karnofsky Score	X													
Height	X													
Weight	X		X	X	X	X	X	X	X	X	X	X	X	X
Signs/Symptoms/ Diagnoses			X	X	X	X	X	X	X	X	X	X	X	X
Concomitant/TB/ ARV Medications			X	X	X	X	X	X	X	X	X	X	X	X
Complete Blood Count with Differential	X		X							X		X		X
Complete Blood Chemistry Profile	X		X							X		X		X
CD4+ Count (HIV-infected participants)	X													
Pregnancy Test	X 		X											
NAT2 genotype (blood and saliva)			X											
Chest X-ray	X 													
Spot Sputum Collection			X 											
Genotypic DST			X											

Evaluation	Screening	Pre-entry	Entry: Registration/ Randomization	Study Treatment (Days)							Discharge	Final Visit	Premature Discontin- uation	
				Step 2 Day 0	1	2	3	4	5	6	7			
(MTBDRs) 														
Overnight Sputum Collection		X	X		X	X	X	X	X	X	X			
EBA Analysis by Solid Culture CFU Determination and Liquid MGIT Culture for TTD 		X	X		X	X	X	X	X	X	X			
Pharmacokinetic Sampling										X				
Hospitalization	X 	X	X		X	X	X	X	X	X	X			

Participants must have a negative serum or urine pregnancy test within 7 days prior to entry.

A chest x-ray is not required at screening if results of a chest x-ray performed within 14 days prior to screening are available.

Sputum from Step 1 (Screening or Day 0) may be used if there is an adequate amount for genotypic DST.

For those participants who have MDR-TB identified by MTBDRplus.

X's here refer to the date that the overnight sputum collection was begun. Assay will be conducted the next morning.

At the discretion of the investigator, some participants may be hospitalized during the screening evaluations, but this is not a requirement.

## 4.3 Analyses of Outcomes Measures

### 4.3.1 Primary outcomes

This is a per-protocol analysis in the efficacy population defined in Section 3.1. The primary endpoint is EBA0-7(CFU), which is defined in Section 3.2. Descriptive statistics of EBA0-7(CFU) with N, mean (s.d.), median (IQR), min, and max for each of the cohorts will be reported. Box plot of EBA0-7(CFU) with Q1, median, mean, and Q3 and plot with 95% confidence intervals for the mean EBA0-7(CFU) will be created for each cohort. Note: The analysis for this outcome will be performed for Group 1 and Group 2.

Another primary endpoint is EBA0-7(TTD), which is defined in Section 3.2. Descriptive statistics of EBA0-7(TTD) with N, mean (s.d.), median (IQR), min, and max will be reported by each cohort. Box plot of EBA0-7(TTD) with Q1, median, mean, and Q3 and plot of 95% confidence interval for the mean EBA0-7(TTD) will be created for each cohort.

New grade 2 or higher signs and symptoms, as well as laboratory events will be summarized in a table using SMR. In addition, all new grade 2 or higher signs/ symptoms and laboratory events with relatedness of treatment and most related drugs.

The PK analysis to examine the relationship between the AUC/MIC and the EBA as described in the protocol Section 9.2.1.2 will be provided in a separate PK analysis plan.

